8.1.9 Causality of Adverse Events

The investigator is responsible for the assessment of the causality of an AE and the sponsor's MM will also assess SAE causality, independent of the PI.

The following guidelines are provided for this assessment:

[figure not shown]
- **Unrelated:** No relationship between the IP and the reported event. The event will be considered “not related” to the IP.
- **Possibly related:** The event follows a reasonable temporal sequence from the time of administration of IP and/or follows a known response pattern to the IP but could also have been produced by other factors.
- **Probably related:** A reasonable temporal sequence of the event with administration of IP exists and based on the known response to the IP, known or previously reported adverse reactions to the IP or similar products, or in the PI's (or designee) clinical judgment the association of the event with the IP seems likely.
- **Definitely related:** A clinical event, including laboratory test abnormality, occurring in a plausible time relationship to IP administration, and which cannot be explained by concurrent disease or other drugs or chemicals.

If the relationship between the AE and the IP is determined to be “possible” “probable,” or “definitely”, the event will be considered to be “related” to the IP.

8.2 Methods and Timing for Assessing, Recording, and Analyzing Safety Parameters

For reporting of solicited AEs, unsolicited AEs, SAEs/AESI/MAAEs please see Sections [8.1.1](#), [8.1.5 – 8.1.7](#).

Figure 3 Adverse Event Period of Reporting

Occurrence of SAEs will be monitored throughout the study and will cover all participating individuals. Study participants will be provided with a 24-hour telephone number to contact study personnel in case of an untoward reaction.

8.2.1 Safety Laboratory Tests

Not applicable.

8.2.1.1 Drug Screen

Not applicable.

8.2.1.2 Alcohol Screen

Not applicable.

8.2.1.3 Viral Testing

At the Screening Visit, blood samples will be collected for serum testing for HBsAg, HCV antibody, and HIV-1/HIV-2 antigen/antibodies. If HCV antibody is positive HCV RNA testing can be performed.

8.3 Reporting Requirements for Immediately Reportable Events

8.3.1 Principal Investigator's Reporting Requirements

The following events must be reported within 24 hours of awareness by the PI (or designee) to the sponsor:

- Any SAE regardless of causal association with the IP.
- Any AESI regardless of causal association with the IP.

Applicable events must be entered into the validated EDC system. In the event of a system failure, the appropriate forms (listed below) will be completed and sent by email to the following address:

Global Pharmacovigilance Department

Emergent BioSolutions Inc.

The paper reported SAEs and AESI should be entered in EDC once the system is available.

For SAEs/AESIs, the Serious Adverse Event/Adverse Event of Special Interest Report Form will be completed (abbreviated hereafter SAE/AESI Report Form). The SAE/AESI Report Form is NOT the same as the AE eCRF. Participant identifiers (eg, name, address, telephone number, social security number, medical record number, or hospital/laboratory number) must be redacted from the source documentation.

All SAEs that are unexpected (eg, adverse drug reactions) must be reported to the IRB by the PI (or designee) as required by ICH GCP E6(R2).

The PI is responsible to notify their IRB according to their policy.

8.3.2 Sponsor's Reporting Requirements

As specified in 21 CFR 312.32, SUSARs will be reported by the sponsor of the IP to the FDA and to all participating investigators in an individual case safety report as soon as possible, no later than 15 calendar days after the sponsor becomes aware of the suspected adverse reaction (21 CFR 312.32(c)(1)). In addition, any unexpected fatal or life-threatening suspected adverse reaction will be reported to the FDA no later than seven days after the sponsor's initial receipt of the information in accordance with 21 CFR 312.32(c)(2). All SAEs that are unexpected (e.g., adverse drug reactions) must be reported to the IRB as required by ICH GCP E6(R2).

8.4 Follow-up of Adverse Events

All AEs, MAAEs, SAEs, and AESI will be followed until resolution, stabilization, or up to 30 days after the last study visit.

8.4.1 Follow-up of Nonserious Adverse Events

Nonserious AEs that are identified from the time IP administration through the 28-day post-IP administration period and are still ongoing on the last scheduled visit must be recorded on the AE eCRF with the current status noted. All nonserious events that are ongoing at this time will be recorded as “Not Recovered/Not Resolved” on the AE eCRF. The status of ongoing, previously reported AEs will be subject to active follow-up.

8.4.2 Follow-up of Serious Adverse Events or Adverse Events of Special Interest

This study requires that participants be monitored for SAE/AESI up to Day 183 End of Study Visit.

The PI will provide or arrange appropriate care for participants for whom SAEs or a potential AESI are experienced. Withdrawal of participants from the study to treat SAEs/AESI is at the discretion of the treating PI. See Section [4.3](#) Participant Withdrawal Criteria.

All SAEs/AESI will be followed by the PI until at least one of the following conditions is met:

- The SAE/AESI is resolved or stable if expected to remain chronic.
- The participant is referred to a specialist or other physician for treatment and follow-up. The PI (or designee) will follow the participant’s condition even if the participant is seen by another physician, to obtain information about the diagnosis and outcome and any treatments and medications administered for the event.

The following will be considered acceptable reasons for discontinuation of follow-up of ongoing SAEs/AESI:

- Participant withdraws consent
- Participant is referred to appropriate long-term medical care
- Participant is considered LTF

It is expected that the investigational site will obtain supporting medical records from appropriate physicians and record this information on the SAE/AESI Report Form and AE eCRF. Additional information received related to any SAE/AESI must be forwarded within 24 hours of awareness to the Emergent Global Pharmacovigilance Department.

8.4.3 Follow-up of Pregnancies

Not applicable, as study population is ≥ 65 years of age.

8.4.4 Unanticipated Problems

For investigational sites in the US, as outlined by the Office for Human Research Protection, unanticipated problems must be reported to the IRB according to the requirements of 45 CFR Part 46. Unanticipated problems are considered to include any incident, experience, or outcome that meets **ALL** the following criteria:

- Unexpected (in terms of nature, severity, or frequency) given:
 - Procedures that are described in the study-related documents, such as the IRB approved research protocol and informed consent document.
 - The characteristics of the participant population being entered into the study.
- Related or possibly related to participation in the study which means there is a reasonable possibility that the incident, experience, or outcome may have been caused by the sample collection.
- Suggests that the study places participants or others at a greater risk of harm (including physical, psychological, economic, or social harm) than was previously known or recognized.

An incidence, experience, or outcome that meets the three criteria above generally will warrant consideration of substantive changes in the study or informed consent process/document or other corrective actions in order to protect the safety, welfare, or rights of participants or others.

The PI should promptly notify the IRB when an unanticipated problem involving risks to participants or others is identified. Also, the PI should notify the sponsor of unanticipated problem(s).

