1.8 Summary of Known and Potential Risks and Benefits

1.8.1 Risks Related to Study Intervention

The injection of PXVX0317, like other injections, can cause pain, redness, or swelling at the injection site. These types of reactions are generally mild. Less commonly, it can cause itching, bruising, or infection.

Most solicited AEs reported by participants enrolled in study PXVX-CV-317-001 were mild to moderate in severity. The percentage of participants who reported \geq Grade 3 AEs for the following categories were as follows: any AEs (7.9%), any solicited AE (6.1%), any systemic solicited AE (5.9%), any local solicited AE (0.2%), any unsolicited AE through Day 57 (2.9%), any treatment-related solicited AE (3.6%), any treatment-related systemic solicited AE (3.4%), any treatment-related local solicited AE (0.2%). There were no reports of \geq Grade 3 treatment-related unsolicited AEs through Day 57. No participants had a treatment-related SAE, and no participants permanently discontinued study due to AE or died during the study.

Among participants from PXVX-CV-317-001 Group 8 (n=50) participants who received the 40 μ g adjuvanted dose selected for further development, 48.0% reported solicited AEs occurring within seven days postvaccination with active vaccine at Day 29. Approximately 22% of participants reported solicited systemic AEs and 40.0% reported solicited local AEs. Solicited local AEs reported included only injection site pain; no injection site redness or swelling was reported after receipt of the active dose. Solicited systemic AEs reported included malaise (4.0%), fatigue (4.0%), headache (8.0%), myalgia (12.0%), nausea (4.0%), and joint pain (2.0%).

There were 13 unrelated SAEs reported for 10 participants in study PXVX-CV-317-001 and study EBSI-CV317-002. One case of anaphylaxis occurred on study Day 309 in a participant that was suspected to be due to a nut allergy. No participants had a treatment-related SAE, and no participants permanently discontinued study due to AE or died during the study.

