1.8.5 Risks to Confidentiality

Efforts will be made to keep participants' personal health information confidential. To maintain confidentiality, paper study records will be stored in a secure location such as a locked office or locked cabinet. Electronic data will be password protected. Electronic study records and samples taken will be coded with a number, not the participants' names. Records will only be shared with authorized personnel and only in connection with carrying out the obligations related to the study.

Although efforts are made to protect the research study records, there is always a risk that someone could get access to the personal information in research records or other information researchers have stored about participants.

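### Protocol 8.4.4 defines study-relatedness as caused by sample collection, so its written test for prompt IRB notice misses vaccine, handling and data problems that are not unexpected SAEs

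*Protocol*

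**What the plan says.** Section 8.4.4 of the protocol opens with a general duty: at US sites, unanticipated problems go to the IRB under 45 CFR Part 46. It then gives a working definition. "Unanticipated problems are considered to include any incident, experience, or outcome that meets" all of three criteria:

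1. The event is unexpected in nature, severity or frequency, given the study documents and the population.
2. It is study-related. This criterion begins "Related or possibly related to participation in the study which means" and continues "there is a reasonable possibility that the incident, experience, or outcome may have been caused by the sample collection".
3. It suggests that participants or others face more risk than was previously known, with harm taken to include physical, psychological, economic and social harm.

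The section says that an event meeting the three criteria will generally warrant considering substantive changes to the study or the consent process. It then states the action: "The PI should promptly notify the IRB when an unanticipated problem involving risks to participants or others is identified". A further sentence asks the investigator to tell the sponsor as well, without a time limit.

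The neighbouring rule in Section 8.3.1 is narrower: "All SAEs that are unexpected (eg, adverse drug reactions) must be reported to the IRB by the PI". The same section sends all SAEs and AESI to the sponsor within 24 hours, and ends by making the investigator responsible for notifying the IRB according to that IRB's policy.

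**The concern.** The words that join the two halves of the second criterion make the second half a definition, not an example. A broad idea, participation in the study, is thereby reduced to one procedure. That would suit a study whose only intervention is a blood draw. Here, each participant receives one intramuscular dose of vaccine or placebo (Section 3.1).

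Section 8.4.4 is where the protocol links an unexpected problem to prompt IRB notice and possible changes to the study or consent form. If its relatedness test excludes the main exposure, a site that follows the text closely has no protocol trigger to tell its IRB about, for example, an unexpected non-serious vaccine effect or a loss of confidential data. Section 1.7 says that the vaccine has not previously been evaluated in this age group, so unexpected findings of that kind are ones on which an IRB would want information.

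**Working it through.** No arithmetic applies. The check sets the definition beside the rest of its own section, the risks the protocol names, and the other reporting routes.

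**Within Section 8.4.4.** The opening words of criterion 2 cover anything arising from participation. Criterion 3 covers economic and social harm, and harm to people other than participants. Sample collection alone is a poor match for that range of harms. The definition is therefore narrower than the text on either side of it.

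**Against the named risks in Section 1.8.**
- Section 1.8.1: "The injection of PXVX0317, like other injections, can cause pain, redness, or swelling at the injection site". Not caused by sample collection.
- Section 1.8.2, allergic reaction to the vaccine. Not caused by sample collection.
- Section 1.8.3, blood draws. Covered. The screening-test consequences in Section 1.8.3.1 are arguably covered too, since they follow from a sample.
- Section 1.8.5: "there is always a risk that someone could get access to the personal information in research records". Not caused by sample collection.

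**Against the other reporting routes.** Assume that each event below is unexpected and suggests increased risk, so that criteria 1 and 3 are met and only criterion 2 is in question.

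| Event | Criterion 2 as written | Other express route to IRB | Express route to sponsor |
|---|---|---|---|
| Harm from a blood draw (Screening, Day 1, 15, 22 or 183) | Met | Not needed | 8.4.4 |
| Unexpected SAE caused by the vaccine | Not met | 8.3.1 | 8.3.1, within 24 hours |
| Non-serious AESI caused by the vaccine | Not met | None | 8.3.1, within 24 hours |
| Other unexpected non-serious vaccine effect | Not met | None | AE recording (3.2.9, 3.2.10, 8.4.1) |
| Dose given after a storage excursion, no SAE | Not met | None | 5.1.4, excursion reported promptly |
| Wrong treatment given, no SAE | Not met | None | Protocol deviation (SAP 2.3.2); ongoing sponsor review (10.7) |
| Unauthorised access to personal data | Not met | None | None found, unless logged as a deviation |

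Section 10.7 does require immediate notice to sponsor and IRB, but only for a deviation made to remove an immediate hazard, which is none of these cases. The Safety Monitoring Committee review in Sections 3.5 and 8.5 is of aggregated blinded data after the first 50 participants, with later reviews at the committee's discretion. It is not a route from site to IRB.

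The table shows one consistent gap. Except for blood-draw harm and unexpected SAEs, the IRB column has no express entry. The sponsor column is nearly full.

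**The case against.** The strongest reply is that the list in Section 8.4.4 does not stand alone. The section first imposes a reporting duty under 45 CFR Part 46, and the list is introduced as what unanticipated problems include, so it need not be exhaustive. Section 8.3.1 adds that the investigator notifies the IRB under its own policy. That sentence sits under immediately reportable events, so its reach is arguable, but its wording is not limited to SAEs. Section 12 also requires compliance with GCP and federal regulations. A careful site would probably report a serious vaccine-handling failure or data breach whatever criterion 2 says.

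This stands as a limit on the reach of the point. A reader might infer that a problem caused by the vaccine can never reach the IRB. The documents do not support that: it is true of the written three-part test, not of all IRB reporting.

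A reader might also infer that the sponsor is left uninformed. That is not supported either. Excursions, deviations, SAEs, AESI and recorded adverse events reach the sponsor by other sections, and the word promptly in 8.4.4 attaches to the IRB notice only.

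Nor does the wording remove every non-serious problem among the 400 planned participants from IRB view. Criteria 1 and 3 would already screen out expected events such as ordinary injection-site reactions.

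None of this makes the definition correct. The general duty and IRB policy help only if the site sets aside the protocol's own meaning of related, and a protocol should not depend on that.

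**Conclusion.** The point holds as a wording error in an operative reporting rule. Read as written, the relatedness definition contradicts its own opening words, the scope of the third criterion and the risks in Section 1.8. The affected set is limited to problems that are unexpected, suggest increased risk, are not unexpected SAEs, and arise from the investigational product, its storage or administration, or data handling. For those, the three-part test does not give the prompt IRB notice that the section is meant to provide.

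The size cannot be stated as a count, because the documents give no expected rate for such events. The gap lies mainly in IRB notice, with confidentiality breaches the one case where no express sponsor route was found either.

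The conclusion rests on a literal reading of the definition and on the current protocol text. It assumes nothing about the content of 45 CFR Part 46 or of individual IRB policies, which are not in the documents. How the phrase came to be there is not stated and does not matter to the point. No endpoint, population, error rate or other part of the statistical analysis is affected.

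**What to change.** In the second criterion of Section 8.4.4, replace the closing words about sample collection so that the event may have been *caused by the investigational product or any study procedure, including IP storage, preparation and administration, sample collection and data handling*. Leave the first and third criteria as they are. This brings the definition into line with its own opening words and with Section 1.8, and it keeps the blood-draw risks covered.

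The cost is one phrase in the next amendment under Section 13.2, a line in site training, and possibly a few more IRB notices. The SAP needs no change.

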8.5 Safety Data Monitoring

An independent SMC will provide safety oversight. The SMC will review aggregated, blinded safety data after the first 50 participants have completed at least seven days of safety follow-up. The remaining participants will be enrolled following the safety review by the SMC and based on the sponsor's consideration of the SMC's recommendation. Any further safety reviews will be at the discretion of the SMC and per the SMC Charter.

9 STATISTICAL CONSIDERATIONS

This section is a summary of the planned statistical analyses. The details are described in the study Statistical Analysis Plan (SAP).

9.1 Sample Size Rationale

Based on the data from the phase 2 study (protocol PXVX-CV-317-001), the seroresponse rate for PXVX0317 vaccine is expected to be approximately █ vs <5% for the placebo participants. With an assumed 10% rate of nonevaluable participants, the power to show

superiority over placebo with 180 PXVX0317 vaccine and 180 placebo evaluable participants is >99.9% for the combined age groups.

The difference in seroresponse rate between PXVX0317 and placebo groups that is considered clinically relevant is █. With 180 baseline seronegative PXVX0317-treated participants and a target seroresponse rate of █ vs a rate of 5% for placebo, the width of a two-sided 95% CI would be $\pm 5.4\%$. If the target PXVX0317 seroresponse is █, the width would be $\pm 6.9\%$. Therefore, the difference in seroresponse rates must be above █ for the lower bound of the 95% CI for the difference to be █.

9.2 Analysis Populations

Analysis will be based on the following study populations:

Enrolled Population: All screened participants who sign an ICF, are entered in the EDC database, and meet all eligibility criteria.

Randomized Population: All screened participants who provide informed consent and provide demographic and other screening measurements and are randomized in the EDC.

Exposed Population: All participants in the randomized population who receive IP.

Safety Population: All participants in the exposed population who provide safety assessment data. Safety endpoints will utilize the safety population, analyzed as treated.

Modified Intent-to-Treat population: All randomized participants who are vaccinated and have at least one postinjection anti-CHIKV SNA titer result, analyzed as randomized.

Immunogenicity Evaluable Population: All participants in the mITT population who: i) provide evaluable serum sample results for the Day 22 time point within the required time frame of Day 19 through Day 27, inclusive, ii) have no measurable anti-CHIKV SNA at Day 1, iii) have no important protocol deviation or other reason to be excluded as defined prior to unblinding. The IEP is the primary population for all immunogenicity analyses.

9.3 Statistical Methods

Tables will be displayed by treatment group (PXVX0317 and placebo) columns for the analysis populations described in Section 9.6.

Continuous endpoints will be summarized by descriptive statistics including number of nonmissing observations (n), mean, standard deviation, median, minimum, and maximum. In the analysis of the human SNA assay data as a continuous variable, anti-CHIKV SNA NT₈₀ values will be logarithmically transformed (base₁₀), and the GMTs and associated 95% CIs for each treatment group will be computed by exponentiating the corresponding log-transformed means and two-sided 95% CIs. Categorical variables will be summarized by frequency counts (n) and percentages of participants (%) in each category, including missing or unknown when appropriate.

9.4 Multiplicity Controls

9.4.1 Coprimary Immunogenicity Endpoints

The familywise error rate will be fixed at a two-sided alpha of 0.05 by the requirement that both coprimary immunogenicity endpoints must be met for a successful outcome:

1. Day 22 seroresponse in the IEP across all age groups combined, including superiority to placebo and the success criterion of the lower bound of the two-sided Newcombe hybrid score method 95% CI on the difference in seroresponse rates between PXVX0317 and placebo [REDACTED].
2. Day 22 GMTs significantly different between PXVX0317 and placebo in the IEP across both age groups combined using an ANOVA model with logarithmically transformed anti-CHIKV SNA titers (\log_{10}) as the dependent variable and treatment group and study site as the fixed effects with a two-sided significance level of 0.05.

9.4.2 Key Secondary Immunogenicity Endpoints

A prespecified hierarchical approach will be employed for the key secondary immunogenicity endpoint hypothesis testing to preserve the type I error rate without the need for further multiplicity adjustment. If the null hypotheses are rejected for both coprimary endpoints, only then will the key secondary endpoints be formally tested in sequential order. If a nonsignificant test is reached formal testing will stop, and the remaining endpoints will be reported for information only. The seroresponse rates and rate differences at Days 15 and 183 will be tested sequentially in order, each for the IEP across both age groups combined, as follows:

1. Day 15 seroresponse superior to placebo.
2. Day 183 seroresponse superior to placebo.

After testing the coprimary immunogenicity endpoints and, if both met, the hierarchical key secondary immunogenicity endpoints, no other formal hypothesis testing will be carried out. The remaining secondary immunogenicity endpoints including GMTs, GMFI, other titers, the exploratory endpoint, and all safety endpoints will be evaluated and reported for information only, thus no further multiplicity adjustment is needed.

